#### 2.3.7.4 JUSTIFICATION OF CONTROL AND EXPIRMENTAL GROUP SUCCESS RATES

Based on multiple imputation and including N=150 Simplify Disc subjects and N=117 historical controls, the Month 24 PS adjusted success rates were estimated to be 93.0% and 73.6%, respectively, for a group difference of 19.4% (90% LB CI 10.9%). The lower bound of the 90% 2-sided CI is equivalent to the lower bound of the 95% 1-sided non-inferiority CI. In the completer's analysis set, 132 of 142 Simplify Disc subjects achieved Month 24 overall success, and 68 of 96 Controls achieved Month 24 overall success.

#### 2.3.7.5 SAMPLE SIZE ANALYSIS

For the purposes of sample size calculation, it is estimated that 85% of the estimated 142 Simplify Disc subjects (N=121) who are not terminal failures or lost to follow-up by Month 24 will be available at year 5. It is estimated that 60% of the estimated 106 (N=64) Control subjects who are not terminal failures or lost to follow-up by Month 24 will be available at year 5.

Based on these results, it was conservatively estimated that the 5-year overall success rates would be 70% of the observed rates, that is, 65% and 50% for Simplify Disc and historical ACDF control, respectively. If the success rates in both groups are larger, statistical power will be larger and so this power analysis would be conservative. With sample sizes of 121 and 64, and assuming 65% and 50% success, the power to detect non-inferiority is 96% at a one-sided 0.05 significance level.

### **2.3.7.6 SUPERIORITY TESTING**

If the non-inferiority study success criterion is met, superiority testing will be performed in the primary analysis set. It will be concluded that the Simplify Disc is superior to the ACDF control if the PS-quintile adjusted one-sided p-value determined from the multiple imputation is less than 0.05.

#### 2.3.7.7 ADDRESSING MISSING PRIMARY OUTCOME DATA

Because of the availability of subject level data in controls that correspond to the subject level data to be collected in the prospective study, missing data will be addressed in the same fashion to how missing data would have been addressed in a randomized clinical trial. Multiple imputation will be used to impute missing final NDI in patients otherwise evaluable for primary CCS. For each of 20 imputed data sets, the primary PS stratified device group difference will be made resulting in a standard error for each. The final device group difference will be the average of the multiple imputed datasets and its standard error will account for both within (usual) and between imputation error.

In addition to multiple imputation, sensitivity analysis will be provided based on tipping point analyses. These are analyses in which all possible combinations of successes and failures are assumed for patients missing primary CCS and the fraction of scenarios in which the statistical conclusion changes is summarized. Best case and worst case, all missing success, and all missing failures scenarios will also be summarized.

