## 2.3.6.2 STUDY EVALUATIONS, PROCEDURES AND ASSESSMENTS

Follow-up evaluations annually at Month 36, Month 48, and Month 60 will include:

- AP and lateral X-rays (plain films);
- Flexion-extension X-rays (used to determine range of motion);
- Lateral bending films (Simplify Disc only);
- Radiographic core lab evaluations;
- Dysphagia Handicap Index (Simplify Disc only);
- NDI assessment;
- SF-12v2 Health Survey (Simplify Disc only);
- VAS pain assessments (neck and arm; neck, left arm and right arm (Simplify Disc only));
- Neurologic evaluation;
- Study related medication status (Simplify Disc Only);
- Work status;
- Treatment satisfaction assessment and
- Adverse events as defined by Section 2.3.8 of this protocol.
- •

Neurologic status will be evaluated by a qualified evaluator, who may be an MD, DO, an RN or a PA. The neurologic evaluation will include a motor and sensory assessment, reflex responses and the determination of the presence or absence of dysphagia, dysphonia, clumsiness, foot drop, atrophy, cramping, muscle spasms, numbness and gait abnormality.

Muscle strength will be graded for the deltoid (C5), biceps (C6), and triceps (C7) according to a 6point scale where 0 = no movement, 1 = trace of muscle contraction; 2 = active movement without gravity; 3 = active movement against gravity; 4 = active movement against gravity/resistance; and 5 =normal response.

Study related medication status will include only medications taken or administered for the following

- Pain (any type);
- Inflammation (any type);

- Muscle relaxation;
- Numbness &/or tingling;
- Hormonal replacement therapy and
- Other medications related to or given for the subject's spinal condition.

All radiographic endpoints will be evaluated independently by one core laboratory.

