# 2.3.7 STATISTICAL CONSIDERATIONS

#### 2.3.7.1 PRIMARY ENDPOINT

The study hypothesis is that in subjects with intractable radiculopathy (arm pain and/or a neurological deficit) with or without neck pain or myelopathy due to a single-level abnormality localized to the level of the disc space at one level from C3 to C7 that is unresponsive to conservative management or have the presence of progressive symptoms, the Month 60 composite clinical success (CCS) rate of the Simplify Disc will be no worse than conventional ACDF when success of ACDF is evaluated at Month 60. Individual success for Simplify Disc and the historical control ACDF is defined as follows:

- Improvement on the NDI of at least 15 percentage points compared to baseline in the Simplify Disc IDE study, and
- No device failures by Month 60, and
- No subsequent surgical procedure at the index level (including revision, removal, reoperation, or supplemental fixation) by Month 60.

Device failure is defined as breakage, migration, or mechanical failure of the components as defined in the Radiographic Evaluation Protocol. Failure of the allograft will not be counted as device failure in the historical ACDF control group.

Per FDA Guidance for the Preparation of IDEs for Spinal Systems, the following definitions apply for the PAS:

- Reoperation any surgical procedure at the index level that *does not involve* modification, addition or removal of any components of the device" in the postoperative or follow-up period.
- Revision any procedure in the postoperative or follow-up period that adjusts modifies or removes part of the original implant configuration *with or without* replacement of a component – may include adjusting the position of the original configuration in the postoperative or follow-up period.
- Removal a procedure where the entire device is removed with or without replacement of the device in the postoperative or follow-up period.

• Supplemental fixation – a procedure in which additional instrumentation not under study is implanted (e.g., supplemental placement of a rod/ screw system).

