#### **2.3.7.8** ANALYSIS OF SECONDARY ENDPOINTS AND ADVERSE EVENTS

Secondary effectiveness endpoints will be compared between groups over time using group differences and 95% confidence intervals for group differences. Adverse events will be summarized by event counts and per subject incidence rates for categories of AE, for specific AEs, by relationship to device and procedure, and for SAEs. Counts will also be summarized by time of onset category and by AE severity. Where applicable, AE summary tables will include 95% confidence intervals for group differences in incidence rates.

For each study group and for important subgroups separately, the primary outcome (i.e., patient success) and secondary endpoints, as well as the incidence of specific complications, will be tabulated and presented by follow-up interval. Comprehensive tables will provide frequency and percentage distributions and descriptive statistics as appropriate in total and for each study group separately. Tables and graphical displays will be provided for both the primary effectiveness and safety populations as appropriate.

Survival analysis methods will be used to describe time to event outcomes including time to secondary surgical intervention.

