# 2.4 RISK ANALYSIS

### 2.4.1 RISKS

No physical risks are anticipated as a result of participation in the long-term follow-up study. The amount of radiation exposure to subjects is relatively small.

Subjects may require additional surgery at the treated spinal level:

- Reoperation any surgical procedure at the index level that *does not involve* modification, addition or removal of any components of the device" in the postoperative or follow-up period.
- Revision any procedure in the postoperative or follow-up period that adjusts modifies or removes part of the original implant configuration *with or without* replacement of a component – may include adjusting the position of the original configuration in the postoperative or follow-up period.
- Removal a procedure where the entire device is removed with or without replacement of the device in the postoperative or follow-up period.
- Supplemental fixation a procedure in which additional instrumentation not under study is implanted (e.g., supplemental placement of a rod/ screw system)

Risks associated with the use of both the Simplify Disc and control spinal systems are expected to be comparable. All secondary index surgeries will be regarded as failures and reported accordingly.

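### The primary imputation rule covers only a missing final NDI in otherwise evaluable patients; read literally, it keeps lost patients with a recorded failure and omits lost patients without one

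*Combined protocol and SAP*

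**What the plan says.** Section 2.3.7.1 makes CCS a three-part endpoint: NDI improvement of at least 15 percentage points, no device failure by Month 60, and "No subsequent surgical procedure at the index level (including revision, removal, reoperation, or supplemental fixation) by Month 60". Section 2.4.1 adds: "All secondary index surgeries will be regarded as failures and reported accordingly". Under Section 2.3.6.2.3, a Simplify subject with index-level surgery leaves the study after the next visit, so the failure is on record before departure.

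For missing outcomes in the primary analysis, Section 2.3.7.7 gives one operational rule: "Multiple imputation will be used to impute missing final NDI in patients otherwise evaluable for primary CCS". Patients whose CCS itself is missing appear in that section only under the tipping-point and best/worst-case sensitivity analyses. The section opens with a general statement that "missing data will be addressed in the same fashion to how missing data would have been addressed in a randomized clinical trial".

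The imputation-based p-value decides non-inferiority (Section 2.3.7.2, margin 0.10, one-sided 0.05). If that succeeds, "superiority testing will be performed in the primary analysis set" (Section 2.3.7.6). Section 2.3.7.8 speaks of displays "for both the primary effectiveness and safety populations as appropriate".

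Section 2.3.7.5 expects 85% of 142 Simplify subjects (121) to be available at year 5. For controls: "It is estimated that 60% of the estimated 106 (N=64) Control subjects" are expected to be available.

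**The concern.** A patient lost at Month 36 with no event has unknown Month 60 status on two of the three CCS components, so is not plainly evaluable apart from NDI. A patient who had index surgery and then left is already a CCS failure. If the rule is programmed as written, the lost patients who re-enter the primary analysis are exactly those who failed. That lowers the observed success rate in each arm, and lowers it more in the arm with more loss. Planned loss is 15% for Simplify and 40% for ACDF, so the distortion need not cancel, even when loss has nothing to do with outcome.

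The opposite shortcut is also imperfect. Imputing NDI alone and treating unknown failure status as failure-free overstates success, more so in the arm with more loss. That gives a smaller bias the other way.

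**Working it through.** **Plan's own figure.** Inputs from Section 2.3.7.5: 121 and 64 subjects, 65% and 50% success, one-sided 0.05; margin 0.10 from Section 2.3.7.2. SE = sqrt(0.65×0.35/121 + 0.50×0.50/64) = 0.0761. Power = Φ((0.15 + 0.10)/0.0761 − 1.645) = 95.0% (Farrington-Manning 95.3%). The stated 96% is reproduced to about one point.

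**Planned loss.** 142 − 121 = 21 (15%); 106 − 64 = 42 (40%).

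**Assumption.** Let k be the share of lost patients with a device failure or index-level surgery on record before loss. The documents do not give it. Loss is taken as independent of outcome.

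**Rate under the literal rule.** Retained patients contribute their outcomes; of the lost, only the share k is kept, all as failures:

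rate = retained × p / (retained + lost × k)

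At k = 10%, Simplify is 121×0.65/(121 + 2.1) = 78.65/123.1 = 0.639. ACDF is 64×0.50/(64 + 4.2) = 32/68.2 = 0.469. The difference is 0.170 against a true 0.150.

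| k (both arms) | Simplify | ACDF | Bias toward Simplify (points) |
|---|---|---|---|
| 0 | 0.650 | 0.500 | 0 |
| 2.5% | 0.647 | 0.492 | 0.5 |
| 5% | 0.644 | 0.484 | 1.0 |
| 10% | 0.639 | 0.469 | 2.0 |
| 15% | 0.634 | 0.455 | 2.8 |

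**One-sided error.** Rejection probability = Φ((d + margin)/SE − 1.645), where d is the literal-rule difference and SE is unpooled with n = retained + lost × k.

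- Non-inferiority null, 40% versus 50%, k = 10%: 48.4/123.1 = 0.393 and 0.469, so d = −0.076; SE = 0.0748; Φ(0.024/0.0748 − 1.645) = 9.3%. At k = 5% and 15%: 6.9% and 12.0%.
- Superiority null, 50% versus 50%, k = 10%: 60.5/123.1 = 0.491 and 0.469, so d = 0.022; SE = 0.0754; Φ(0.022/0.0754 − 1.645) = 8.9%. At k = 5% and 15%: 6.8% and 11.3%.

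A simulation of 20,000 trials per setting agrees. With a 20% cumulative failure rate in each arm and uniform event and loss times (k about 10%), error was 9.6% for non-inferiority and 9.3% for superiority. Dropping all lost patients, failures included, gave about zero bias and about 5% error. The selective retention is therefore the cause. Neither calculation models the PS strata.

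**Unequal k, at 65%/50%.** k = 15% Simplify and 5% ACDF: 0.634 − 0.484, a bias of −0.1 points. k = 5% and 15%: 0.644 − 0.455, a bias of +3.9. k = 10% and 2%: 0.639 − 0.493, a bias of −0.5.

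**Does imputing everyone remove it?** Only if the model uses failure status at last contact. Imputing from group alone fills the gaps at the literal-set rate x/n, so the arm rate stays x/n and the bias stays. Conditioning on being failure-free, the unresolved patients succeed with probability p/(1 − k). For ACDF at k = 10% that gives (32 + 42×0.9×0.5/0.9)/106 = 53/106 = 0.50, which is the true rate.

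**The case against.** The strongest reply is that no section says event-free lost patients are dropped. Section 2.3.7.3 carries the PS-selected population forward. Section 2.3.7.4 reports a Month 24 imputation on all 150 and 117 subjects when completers numbered 142 and 96, so 8 and 21 subjects without a completed outcome were brought in. Section 2.3.7.7 promises handling as in a randomized trial. Surgery and device failure are event-type components, so otherwise evaluable could simply mean no failure on record. This stands as evidence of intent. It is not a Month 60 rule, because the general promise is followed by the narrow one, and two programmers could build different primary sets from it.

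A reader might also infer that the plan never defines its analysis sets. The documents do not support that: Sections 2.3.7.9 and 2.3.7.10 are not legible in the public version and could hold the definitions.

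The size rests on k. Section 2.3.7.3 and Section 2.3.7.5 together put terminal failures and losses combined by Month 24 at no more than 8/150 (5.3%) for Simplify and 11/117 (9.4%) for ACDF. A k of 10 to 15% in both arms is therefore a stress case. At k = 0 there is no bias.

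The planned tipping-point and extreme-case analyses would show the sensitivity. They do not change the p-values that decide the two tests.

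**Conclusion.** The concern holds as an ambiguity with a quantifiable consequence, and it should be fixed before the comparison is run. Under the literal reading, with random loss at the planned 15% and 40% and equal k of 5, 10 or 15%, the bias is 1.0, 2.0 or 2.8 points toward Simplify. One-sided error is about 7/9/12% at the non-inferiority null and 7/9/11% at the superiority null. These figures depend on an assumed k and on unstratified calculations.

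Three stronger readings go too far:

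- That the sponsor will discard event-free lost patients. The text allows this but does not say it.
- That the bias must favour Simplify. With more recorded failures among lost Simplify patients it can vanish or reverse.
- That two primary tests are compromised. Non-inferiority alone defines study success, and superiority is a gated follow-on. At 65%/50%, the chance of meeting non-inferiority is about 95% at k = 0 and higher with equal k, so it is robust at planning rates. The exposure is mainly the superiority claim, and error near the margin.

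**What to change.** In Section 2.3.7.7:

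1. State that the primary analysis includes every PS-selected subject in the post-approval comparison set. Say whether that set is the 150/117 of Section 2.3.7.3 or the 142/106 of Sections 2.3.4 and 2.3.7.5, with the same rule in both arms. Use one name for it in Sections 2.3.7.6 and 2.3.7.8.
2. Count any known device failure or index-level surgery by Month 60 as a failure.
3. For every other subject without a known Month 60 CCS, impute CCS (NDI and failure status together) within group, conditional on being failure-free at last contact. Use PS quintile, baseline NDI and available earlier NDI.
4. Keep the otherwise-evaluable analysis as supportive, and keep the planned tipping-point and extreme-case analyses. The change removes the selective-retention bias under random loss; it does not remove dependence on why patients were lost.

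No new data should be needed. The visit schedule in Section 2.3.6.2 ("Follow-up evaluations annually at Month 36, Month 48, and Month 60 will include") lists NDI without restricting it to Simplify, and Section 2.3.7.7 says subject-level control data are available. The cost is SAP wording, some programming and possibly a slightly wider standard error. In a 6,000-run simulation with 20 imputations the mean standard error moved by at most 0.23 points (7.33 to 7.10), and in one setting it rose (7.49 to 7.56). If the sponsor already intends this approach, a few sentences suffice.

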#### 2.3.7.2 STUDY SUCCESS

The null hypothesis is that the probability of achieving Month 60 composite clinical success (CCS) for patients implanted with the Simplify Disc device is no more than 0.10 smaller than the probability of ACDF control patients achieving Month 60 CCS. This study will be considered a success if the PS-quintile adjusted, multiple imputation based, 1-sided p-value for rejecting this null hypothesis is less than or equal to 0.05.

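### With only 20 imputations, a near-threshold verdict, mainly on superiority, can turn on the random seed; more imputations would cost only computing time

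*Combined protocol and SAP*

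**What the plan says.** Section 2.3.7.7 sets the scope of the imputation: "Multiple imputation will be used to impute missing final NDI in patients otherwise evaluable for primary CCS". The number of imputations is fixed: "For each of 20 imputed data sets, the primary PS stratified device group difference will be made resulting in a standard error for each". The estimates are averaged, and of the combined estimate the section says that "its standard error will account for both within (usual) and between imputation error", which is Rubin-type combination.

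Both formal decisions are read from this analysis. Section 2.3.7.2 declares success if the adjusted, imputation-based "1-sided p-value for rejecting this null hypothesis is less than or equal to 0.05". Section 2.3.7.6 then allows a superiority claim if the "PS-quintile adjusted one-sided p-value determined from the multiple imputation is less than 0.05".

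Section 2.3.7.5 gives the only indication of how much data may be missing at year 5. For controls, "It is estimated that 60% of the estimated 106 (N=64) Control subjects" will be available; for Simplify Disc the figure is 85% of 142, or 121.

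The text available states no seed, no limit on Monte Carlo error and no rule for a borderline p-value.

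**The concern.** Multiple imputation is itself a simulation. With a finite number of imputations M, both the averaged group difference and the estimated between-imputation variance carry random error that depends on the seed. The pooled p-value inherits both. When it is set against a fixed cut-off, two analysts who follow the plan exactly on the same data can reach opposite verdicts.

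What is at stake is the reproducibility of a labelled conclusion. A superiority claim that holds under one seed and not another is hard to defend, and with no seed fixed in advance, the choice among seeds is open after the data are seen.

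**Working it through.** **Inputs.** M = 20 (2.3.7.7); one-sided 0.05 for both decisions (2.3.7.2, 2.3.7.6); margin 0.10 (2.3.7.2); available subjects 121 of 142 and 64 of 106, success rates 65% and 50%, stated power 96% (2.3.7.5); Month 24 adjusted rates 93.0% and 73.6% (2.3.7.4).

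**Step 1: the plan's own power.** SE = √(0.65×0.35/121 + 0.50×0.50/64) = √0.005786 = 0.0761. Non-inferiority: (0.15 + 0.10)/0.0761 = 3.29, and Φ(3.29 − 1.645) = 95.0%. A Farrington-Manning null SE gives 95.3%. The stated 96% is reproduced to within about one point. Superiority: 0.15/0.0761 = 1.97, and Φ(1.97 − 1.645) = 63%. So at the planning rates the superiority statistic is centred only 0.33 above its cut-off, while the non-inferiority statistic is centred 1.64 above.

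**Step 2: fraction of missing information (assumption).** If every unavailable subject were imputed from a model without predictors, λ = 1 − (0.2275/142 + 0.25/106)/(0.2275/121 + 0.25/64) = 1 − 0.003961/0.005786 = 0.316. Because the plan does not give the amount imputed or the predictors, I use the range 0.1 to 0.4.

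**Step 3: seed noise in the statistic.** Scale the total variance to 1, so that the within part is W = 1 − λ and the between part is B = λ. The pooled variance is T = W + (1 + 1/M)B. For a statistic near 1.645, the seed-to-seed variance is approximately λ/M + (1.645/2)² × 2[(1 + 1/M)λ]²/(M − 1).

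- M = 20, λ = 0.316: 0.0158 + 0.0078 = 0.0236, SD 0.15.
- M = 200, λ = 0.316: 0.0016 + 0.0007 = 0.0023, SD 0.05.

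**Step 4: how often two seeds disagree.** I simulated 400,000 trials. The infinite-M statistic was drawn from N(1.97, 1) for superiority and N(3.29, 1) for non-inferiority, with seed noise added as above, a chi-square draw for the between variance, and Rubin's t reference. The centres were held fixed across λ.

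| λ | Superiority, M=20 | Superiority, M=200 | Non-inferiority, M=20 | Non-inferiority, M=200 |
|---|---|---|---|---|
| 0.1 | 3.3% | 1.0% | 0.9% | 0.3% |
| 0.2 | 4.9% | 1.5% | 1.4% | 0.4% |
| 0.316 | 6.5% | 2.0% | 1.9% | 0.6% |
| 0.4 | 7.8% | 2.4% | 2.3% | 0.7% |

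Type I error was 5.0% at M = 20 and at M = 200 (λ = 0.316). Superiority power was about 62% and 63%.

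**Step 5: cross-check by imputing the outcome itself.** A second simulation imputed the binary outcome (Beta posterior draw, then binomial imputation) for 21 of 142 and 42 of 106 subjects, without covariates or PS strata. Two seeds disagreed on superiority in 6.2% of trials at M = 20 and 1.9% at M = 200, and on non-inferiority in 1.8% and 0.5%. For single data sets at M = 20:

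- Planning point, 79/121 vs 32/64. Non-inferiority: median p 0.0005, 95% seed range 0.0001 to 0.0022, and no seed in 20,000 exceeded 0.05. Superiority: median p 0.023, range 0.010 to 0.045, and 1.1% of seeds exceeded 0.05. At M = 200 the superiority range narrows to 0.017 to 0.028.
- Borderline, 78/121 vs 33/64: superiority p ranges from 0.023 to 0.081, and 60% of seeds succeed (88% at M = 200).
- Borderline, 79/121 vs 34/64: superiority p ranges from 0.029 to 0.094, and 36% of seeds succeed (21% at M = 200).

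**Step 6: other scenarios, M = 20.** With 20% of controls and 7% of disc subjects imputed, disagreement is 3.6% (superiority) and 0.4% (non-inferiority). At the Month 24 rates it is 1.2% and 0%. If the true rates were equal (assumed 60% each), non-inferiority disagreement would be about 6%.

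**The case against.** Four points can be made for the plan.

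- **Validity is intact.** Rubin's rule with a t reference allows for finite M, and the simulations show no inflation of type I error and only a trivial loss of power. This stands. A reader might infer that the p-value is biased or the test invalid; nothing in the calculations supports that.
- **Study success is barely exposed.** A reader might infer that the main verdict hangs on the seed, because section 2.3.7.2 uses the same p-value. At the plan's own rates it does not: the non-inferiority p-value at the planning point is near 0.0005, and two seeds disagree in about 2% of trials or fewer. Section 2.3.7.5 also presents those rates as conservative. This stands, with the reservation that exposure grows if the true difference is much smaller than planned.
- **The amount imputed is unknown.** A reader might take 40% of controls as the share to be imputed. Section 2.3.7.5 gives that shortfall for sample size only. Section 2.3.7.7 limits imputation to missing final NDI in patients otherwise evaluable, so known surgical or device failures need none, and NDI from Months 36 and 48 (2.3.6.2) could sharpen the model. Conversely, losses before Month 24 among the 117 selected controls could add to the number. This stands, and is why a range is shown.
- **Sensitivity analyses are planned.** Tipping-point and extreme-case analyses would show that a borderline result is fragile. They vary the missing-data assumption, however, and do not measure seed noise, so they do not answer the point.

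It is also fair to say that no threshold singles out 200. Disagreement falls steadily as M rises, and some remains at 200.

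**Conclusion.** The concern holds as a minor weakness in reproducibility, chiefly for the superiority claim. At 20 imputations and the planning rates, two runs of the same plan on the same data would disagree on superiority in roughly one trial in 13 to one in 30; at 200 imputations, in roughly one in 42 to one in 100. When the limiting p-value lies close to 0.05, the verdict at 20 imputations is little better than a coin toss. These sizes rest on the assumed range for the fraction of missing information, on the planning rates, and on simple imputation models without predictors or PS strata. Good predictors or larger true effects would shrink them.

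**What to change.** In section 2.3.7.7, replace 20 with a larger number of imputations, for example at least 200. State the random seed in advance, and report the Monte Carlo standard error of each decisive p-value. A fixed seed alone stops selection among seeds but leaves the verdict resting on an arbitrary number; the larger M is what reduces the noise, here about threefold. An equivalent route is to set a limit on the Monte Carlo error of the p-value and raise M until it is met.

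The cost is one changed number, a sentence or two in the plan, and minutes of computing. Data collection, sample size, hypotheses and margin are untouched.

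### The tipping-point analysis is summarised as a fraction of undefined scenarios; the plan should report where the conclusion tips

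*Combined protocol and SAP*

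**What the plan says.** Section 2.3.7.7 handles missing primary outcomes by multiple imputation: "Multiple imputation will be used to impute missing final NDI in patients otherwise evaluable for primary CCS". As sensitivity analysis it adds a tipping-point exercise in which "all possible combinations of successes and failures are assumed for patients missing primary CCS", and then "the fraction of scenarios in which the statistical conclusion changes is summarized". The next sentence adds four fixed cases: "Best case and worst case, all missing success, and all missing failures scenarios will also be summarized".

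The section does not say whether a combination is one assignment of outcomes to individual patients, one pair of arm totals, or one set of counts within propensity-score quintiles. It gives no weighting, no threshold for the fraction, and no request to report where the conclusion changes.

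The expected extent of missing data comes from section 2.3.7.5. For the device, "it is estimated that 85% of the estimated 142 Simplify Disc subjects (N=121") will be available at year 5. For controls, "It is estimated that 60% of the estimated 106 (N=64) Control subjects" will be.

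**The concern.** A tipping-point analysis should tell the reader how far the missing outcomes must depart from the observed ones before the conclusion changes. The reader can then judge whether such a departure is believable. A share of scenarios does not say this. It gives plausible and implausible scenarios the same weight, and it changes with the definition of a scenario even when the data do not. If the definition is settled only after the data are seen, very different fractions would all comply with the plan.

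This matters more than usual here. The plan expects about 15% of device subjects and 40% of controls to be unavailable at year 5, in a comparison with a non-concurrent control group. The tipping-point exercise and the four fixed cases are the only sensitivity checks on the primary result that section 2.3.7.7 names.

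**Working it through.** **Inputs.** Section 2.3.7.5: 121 of 142 device and 64 of 106 control subjects available, so up to 142 − 121 = 21 and 106 − 64 = 42 missing; assumed success 65% and 50%. Section 2.3.7.2: margin 0.10 ("is no more than 0.10 smaller than the probability of ACDF control patients achieving Month 60 CCS") and level 0.05 ("1-sided p-value for rejecting this null hypothesis is less than or equal to 0.05"). The planned rates correspond to about 79/121 (65.3%) and 32/64 (50.0%) observed successes.

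**The plan's own figure.** Power = Φ((0.65 − 0.50 + 0.10)/SE − 1.645), with SE = √(0.65·0.35/121 + 0.50·0.50/64) = 0.0761. This gives Φ(3.287 − 1.645) = 95.0%, against a stated 96%, which is close enough to confirm the inputs. The plan states no figure for the tipping-point fraction.

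**Enumeration.** Let i be the successes among the 21 missing device subjects and j those among the 42 missing controls. Put p₁ = (79 + i)/142 and p₂ = (32 + j)/106, and z = (p₁ − p₂ + m)/√(p₁(1 − p₁)/142 + p₂(1 − p₂)/106), with m = 0.10 for non-inferiority and m = 0 for superiority. The conclusion holds if z ≥ 1.645. Observed data alone give z = 3.33 and 2.01, so both conclusions hold at the start. The test is unadjusted because the documents give no quintile sizes.

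**Fraction of scenarios that change the conclusion, same data:**

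| Counting unit | Non-inferiority | Superiority |
|---|---|---|
| Arm-total cells, 22 × 43 = 946 | 174/946 = 18.4% | 410/946 = 43.3% |
| Counts within quintiles (missing split about evenly, illustrative) | 1.8% | 33.9% |
| Patient-level assignments, 2⁶³ | 0.0093% | 22.7% |

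For non-inferiority the top and bottom rows differ by a factor of about 2,000. Patient-level counting weights each cell by C(21, i)·C(42, j)/2⁶³. For controls, ΣC(42, j)/2⁴² over j = 15 to 27 is 95.6%, so nearly all scenarios put the missing controls near 50% success. That is the planned observed control rate, so the fraction hardly tests a departure from it.

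**Does the fraction track robustness?** Yes, once the rule is fixed. With controls at 32/64 and device successes of 70, 74, 79 and 85 of 121, the non-inferiority fraction is 34.7%, 27.5%, 18.4% and 9.4% by arm-total cells, and 3.8%, 0.44%, 0.0093% and 0.00002% by patient-level assignments.

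**The boundary.** Smallest number of successes among the 42 missing controls at which the conclusion is lost:

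| Missing device subjects successful | Non-inferiority lost at | Superiority lost at |
|---|---|---|
| 4/21 | 30/42 (71%) | 19/42 (45%) |
| 14/21 | 38/42 (90%) | 27/42 (64%) |

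Check of the 14/21 row, where p₁ = 93/142 = 0.6549:
- Non-inferiority: j = 37 gives z = 1.70 and j = 38 gives z = 1.55.
- Superiority: j = 26 gives z = 1.72 and j = 27 gives z = 1.57.

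With 26 or fewer of the 42 missing controls successful, no device outcome overturns non-inferiority. With all 42 successful, at least 20 of the 21 missing device subjects must succeed to keep it.

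**The four fixed cases.** For non-inferiority, best case (z = 8.55), all failure (5.81) and all success (1.81) hold, and only the worst case (−0.68) fails. For superiority, best case (6.84) and all failure (4.17) hold, while all success (0.10) and worst case (−2.32) fail. These are the corners of the grid; none lies on the boundary.

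**The case against.** Several points on the other side stand.

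- A reader might infer that the fraction reflects counting alone and says nothing about robustness. The documents do not support that: under any one rule the non-inferiority fraction falls steadily as the observed result strengthens. The defect is the undefined unit and the missing location, not an absence of information.
- The four fixed cases are informative. At planning values non-inferiority survives three of them. They bound the result, but they do not show how close the boundary lies to plausible outcomes.
- Nothing in the plan forbids showing the full grid, and section 2.3.7.8 foresees tables and graphical displays as appropriate. But the only summary that section 2.3.7.7 commits to is the fraction.
- A reader might count as missing everyone between the available subjects and the propensity-score sample of 150 and 117 in section 2.3.7.3, that is 29 and 53. The documents do not support this. Section 2.3.7.5 describes the 142 and 106 as excluding terminal failures as well as losses by Month 24; terminal failures have a known outcome, and the split is not given. Even 21 and 42 are upper figures, because subjects with later index-level surgery leave after their next visit (section 2.3.6.2.3) and are already failures by the endpoint definition.
- The planned test is adjusted for quintiles, so arm totals alone do not determine its result. A boundary in arm totals is unique only once the allocation of assumed successes across quintiles is fixed. This is correct, and the fix has to supply that rule.

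**Conclusion.** The concern holds as a weakness in how the sensitivity analysis is reported. With the scenario undefined, the same planning-value data give a non-inferiority fraction anywhere from 0.009% to 18.4%, and a superiority fraction from 23% to 43%. No version of the fraction shows where the conclusion tips.

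The boundary does, and it separates the two claims. With 14/21 missing device subjects successful, losing non-inferiority needs 90% success among missing controls. That is above both the planned 50% and the 73.6% adjusted control rate at Month 24 (section 2.3.7.4). Losing superiority needs 64%, which lies between those two rates and is open to debate.

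The figures assume observed results at the planned rates, 21 and 42 missing as upper values, and an unadjusted Wald test. They illustrate the problem and do not predict the trial's result. A reader might also infer that study success is in doubt. It is not affected by this point: sections 2.3.7.2 and 2.3.7.6 rest both conclusions on the multiple-imputation p-value, and no decision uses the fraction.

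**What to change.** Amend section 2.3.7.7 so that the tipping boundary is the main summary:

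- For each number of successes among missing Simplify subjects, report the smallest number among missing controls at which the PS-quintile-adjusted conclusion changes, for non-inferiority and for superiority.
- State in advance how assumed successes are allocated across quintiles, for example in proportion to the missing subjects in each quintile.
- Show the boundary on a grid, with the observed and imputed success rates of each arm beside it.
- Treat subjects with a known device failure or index-level surgery as failures, not as missing.
- Keep the four fixed cases. The fraction may stay as a supplement if its counting unit is defined.

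The cost is a few sentences of text, the allocation rule, and slightly more reporting. The planned scenario runs already supply most of what is needed, and the primary test does not change.
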